### **7.3 Study Treatment: Visit 3 (Day 14 ± 2)**

Note: Please make every effort possible to have the visit scheduled in the morning so the AM dose can be taken in the morning. Ideally, daily doses should be taken 12 hours apart and no less than 6 hours apart.

The following evaluations will be performed at this visit:

1. Concomitant medications;
2. Symptom-based physical examination;
3. Vital signs;
4. C-SSRS;
5. Blood/urine sample collection:
  - a. Safety laboratory tests; and
  - b. PK - A pre-dose trough sample will be drawn. The exact times of AM dosing and PK sample collections at the site will be documented.
6. 12-lead ECG before dosing drug (trough)
7. Administer study drug at the site;
8. Adverse events;
9. 12-lead ECG 1-1.5 hours post-dose;
10. Blood sample collection: Second PK blood draw 60 minutes ± 30 minutes post-dose; and
11. Dispense study drug.

### **7.4 Study Treatment: Visit 4 (Day 42 ± 3)**

The following evaluations will be performed at this visit:

1. Concomitant medications;
2. Symptom-based physical examination;
3. Vital signs;
4. C-SSRS;
5. Blood/urine sample collection:
  - a. Safety laboratory tests;
6. 12-lead ECG;
7. Adverse events; and
8. Dispense study drug.

### **7.5 Study Treatment: Visit 5 (Day 84 ± 3)**

The following evaluations will be performed at this visit in the following order or as close as possible when feasible:

1. ADAS-Cog 11;
2. MMSE;
3. ADCS-ADL;
4. CDR-SB;
5. Concomitant medications;

6. Symptom-based physical examination;
7. Vital signs;
8. C-SSRS;
9. Winterlight Speech Assessment (only in English speaking (primary language subjects and only in the US and UK);
10. Blood/urine sample collection:
  - a. Safety laboratory tests;
11. 12-lead ECG;
12. Adverse events; and
13. Dispense study drug.

### **7.6 Study Treatment: Visit 6 (Day 126 ± 3)**

The following evaluations will be performed at this visit in the following order or as close as possible when feasible:

1. Concomitant medications;
2. Symptom-based physical examination;
3. Vital signs;
4. C-SSRS;
5. Blood/urine sample collection:
  - a. Safety laboratory tests; and
6. Adverse events.

### **7.7 Study Treatment: Visit 7 (Day 168 ± 3)**

Note: Please make every effort possible to have the visit scheduled in the morning so the AM dose can be taken in the morning. Ideally, daily doses should be taken 12 hours apart and no less than 6 hours apart.

The following evaluations will be performed at this visit in the following order or as close as possible when feasible:

1. ADAS-Cog 11;
2. MMSE;
3. ADCS-ADL;
4. CDR-SB;
5. NPI;
6. Winterlight Speech Assessment (only in English speaking (primary language subjects and only in the US and UK);
7. Concomitant medications;
8. Oral examination and collection of oral biomarker samples (SGP and buccal cell swabs) (only at selected sites);
9. Saliva collection;
10. Symptom-based physical examination;
11. Vital signs;

12. C-SSRS;
13. Blood/urine sample collection:
  - a. Safety laboratory tests;
  - b. PK - A pre-dose trough sample will be drawn and the subject will then take their dose of study drug on-site. The exact times of AM dosing and PK sample collections at the site will be documented.
  - c. Serum and whole blood (PBMCs) for biomarkers;
14. Adverse events;
15. 12-lead ECG before dosing drug (trough);
16. Administer study drug at the site;
17. 12-lead ECG 1-1.5 hours post-dose;
18. Blood sample collection: Second PK blood draw 2 hours  $\pm$  30 minutes post-dose; and
19. Dispense study drug.

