##### Exploratory Endpoints

Exploratory endpoints in all participating subjects include change from screening/baseline and/or Visit 2 to the end of treatment period in the following measures:

- Blood-based biomarkers in serum and peripheral blood mononuclear cells (PBMCs); and
- Saliva biomarkers of *P. gingivalis* infection and inflammation.
- Cerebrospinal fluid:
  - CSF A $\beta$ 42, total Tau, and phosphorylated Tau;
  - Bacterial DNA in the CSF on quantitative polymerase chain reaction (qPCR); and
  - CSF biomarkers.

Exploratory endpoints in subjects participating in sub-studies include change from screening/baseline to the end of treatment period in the following measures:

- Winterlight Speech Assessment (only in English speaking subjects (primary language and only in the US and UK);
- Magnetic resonance imaging sub-study (subjects who have MRIs done in conjunction with the study):
  - Hippocampal volume; and
  - Cortical thickness.

- Clinical periodontitis sub-study (subjects enrolled at selected sites):
  - Pocket Depth (PD);
  - Clinical Attachment Level (CAL) at 6 sites per tooth (distobuccal [DB], buccal [B], mesiobuccal [MB], distolingual [DL], lingual [L], and mesiolingual [ML]);
  - The percentage of sites with Bleeding on Probing (BOP); and
  - Biomarkers of *P. gingivalis* infection and inflammation in subgingival plaque (SGP) and buccal cell swabs.

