### **7.1 Screening: Visit 1 (Day -42 to Day -1)**

During the screening period, the eligibility of subjects will be confirmed according to the Schedule of Evaluations in this protocol (see [Table 1](#)). The following evaluations will be performed at Screening in the following order as close as possible when feasible:

1. Obtain informed consent from subject, and caregiver informed consent signed by the primary caregiver;
2. Past medical history and confirmation of cognitive decline in the last 12 months;
3. Concomitant medications;
4. Inclusion/exclusion criteria for eligibility;
5. Modified Hachinski;
6. Columbia-Suicide Severity Rating Scale (C-SSRS);

7. Mini-Mental State Examination (MMSE). Subjects with MMSE score of 12-24, inclusive, will have the rest of their screening procedures performed or scheduled);
8. Alzheimer's Disease Assessment Scale-Cognitive Subscale 11 (ADAS-Cog 11);
9. Clinical Dementia Rating, Sum of Boxes (CDR-SB);
10. Winterlight Speech Assessment (only in English speaking (primary language subjects and only in the US and UK);
11. 12-lead electrocardiogram (ECG);
12. Weight;
13. Vital signs;
14. Full physical examination, including height and body mass index (BMI) calculation;
15. Urine drug screen;
16. Urine pregnancy test (women of child bearing potential only);
17. Blood/urine sample collection for:
  - a. Serology (Hepatitis C virus antibodies [HCV-Ab], Hepatitis B surface antigen [HBsAg], Human Immunodeficiency Virus [HIV] 1 and 2);
  - b. Apolipoprotein E (Apo E) genotyping;
  - c. Follicle stimulating hormone (FSH) for peri-menopausal (irregular menstrual periods) or post-menopausal (no menstrual period for >12 months) female subjects;
  - d. Vitamin B12
  - e. Thyroid function tests
  - f. Syphilis
  - g. Pregnancy test (only if urine pregnancy test is positive); and
  - h. Safety laboratory tests;
18. Saliva collection;
19. Oral examination and collection of oral biomarker samples (subgingival plaque [SGP] and buccal cell swabs) (only at selected sites); and
20. Magnetic resonance imaging (MRI) of the brain. Computed Tomography (CT) scans of the brain can be used instead of MRIs only in subjects who have an absolute contraindication for MRI.

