Screening procedures can be done on multiple days if needed, with more invasive procedures done after other screening procedures are completed. A screen failure is any subject who signs the informed consent but does not qualify for the study or discontinues the study prior to randomization. A subject can be rescreened if the Principal Investigator thinks the subject may qualify for the study upon rescreening, and if the Medical Monitor agrees.

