### **7.10 Study Treatment: Visit 10/Early Termination (Day 336 ± 8)**

Note: To accommodate the logistics of performing the LP procedure, it may be done up to 7 days prior to V10/Day 336. Please make every effort possible to have the visit scheduled in the morning so the AM dose can be taken in the morning. Ideally, daily doses should be taken 12 hours apart and no less than 6 hours apart.

The following evaluations will be performed at this visit or at Early Termination in the following order as close as possible when feasible:

1. Administer last dose of double-blind study drug at the site;
2. Blood/urine sample collection:
  - a. Safety laboratory tests;
  - b. PK - A single post-dose sample will be drawn from each subject while on-site at the clinic at 4 hours ± 30 minutes post-dose. The exact times of AM dosing and PK sample collections at the site will be documented.
  - c. Serum and whole blood (PBMCs) for biomarkers;
  - d. Pregnancy test (only if urine pregnancy test is positive);
3. Adverse events;
4. Oral examination and collection of oral biomarker samples (SGP and buccal cell swabs) at selected sites (will be completed within 8 days before Visit 10 [or Early Termination] when applicable).
5. 12-lead ECG 1-1.5 hours post-dose
6. MRI of the brain, only in subjects who had a screening MRI performed, and has to be done within 8 days prior to Visit 10. CT scans of the brain can be used instead of MRIs, only in subjects who have an absolute contraindication for MRI;
7. ADAS-Cog 11;
8. MMSE;
9. ADCS-ADL;
10. CDR-SB;
11. NPI;
12. Winterlight Speech Assessment (only in English speaking (primary language subjects and only in the US and UK);
13. Concomitant medications;
14. Symptom-based physical examination;
15. Saliva collection;

16. Weight;
  17. Vital signs;
  18. Lumbar puncture to collect CSF;
  19. Urine pregnancy test (women of child bearing potential only);
  20. C-SSRS;
  21. Informed consent will be obtained for subjects who agree to participate in the open label extension portion of the study; and
  22. Inclusion/exclusion will be evaluated to determine eligibility for subjects who want to participate in the open label extension portion of the study.  
Dispense OLE study drug – subjects who participate in OLE only. The subject should be instructed to take the first dose of COR388 in the morning of the next day.
- NOTE:** Effective 16 February 2021, the OLE portion of the study was terminated by the Sponsor.

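### At dental sites, saliva is listed before the oral examination at Screening but after it at Weeks 24 and 48, which can contaminate the within-arm change in an exploratory salivary biomarker

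*Protocol*

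**What the plan says.** Saliva biomarkers are an exploratory endpoint for all participating subjects (Protocol 4.1.2): "Saliva biomarkers of *P. gingivalis* infection and inflammation". They are assessed as change to the end of treatment, with the reference given as screening/baseline and/or Visit 2. Oral examinations are done only at selected sites (8.12).

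The visit lists carry an order. For Screening (7.1): "The following evaluations will be performed at Screening in the following order as close as possible when feasible". Sections 7.2, 7.7 and 7.10 have near-identical lead-ins. Within these lists:

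- **Screening (7.1):** item 18 is "Saliva collection" and item 19 is "Oral examination and collection of oral biomarker samples (subgingival plaque [SGP] and buccal cell swabs) (only at selected sites"). The section adds: "Screening procedures can be done on multiple days if needed, with more invasive procedures done after other screening procedures are completed".
- **Visit 7, Week 24 (7.7):** item 8 is "Oral examination and collection of oral biomarker samples (SGP and buccal cell swabs) (only at selected sites") and item 9 is saliva.
- **Visit 10/ET, Week 48 (7.10):** item 4 is "Oral examination and collection of oral biomarker samples (SGP and buccal cell swabs) at selected sites", to be completed in the 8 days before the visit where applicable. Saliva is item 15.

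Section 8.11 names the visits at which saliva is taken and leaves the collection procedure to the Laboratory Manual. It sets no order relative to the oral examination.

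**The concern.** The oral examination disturbs the mouth. It probes six sites on each tooth present (8.12.1.2), records bleeding (8.12.1.3), and takes subgingival plaque on paper points from the teeth with the deepest pockets (8.12.2.2). Saliva is then assayed for bacterial DNA and biomarkers (8.11). If probing releases plaque or blood into the mouth, saliva taken just afterwards is not the same kind of sample as saliva taken beforehand.

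At dental sites the listed order gives baseline samples with no same-visit probing before them and a Week 24 sample directly after probing. Part of the change from baseline could then come from the examination. Other sites have no examination, so their saliva would not carry this component and the two site types would not be like for like. At stake is how clearly one of the mechanism biomarkers can be read for a drug aimed at *P. gingivalis*.

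**Working it through.** **Order by visit (list positions)**

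| Visit | Saliva | Oral examination | Listed first |
|---|---|---|---|
| Screening (7.1) | 18 | 19 | saliva |
| Visit 2 (7.2) | 15 | none | – |
| Visit 7, Week 24 (7.7) | 9 | 8 | examination, adjacent |
| Visit 10/ET, Week 48 (7.10) | 15 | 4, up to 8 days before the visit | examination |
| Visit 11 (7.12) | 6 | none | – |
| OLE-6 (7.20, since terminated) | 5 | 14 | saliva |

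So 18 < 19 at Screening and 5 < 14 at OLE-6, but 8 < 9 and 4 < 15 in the opposite direction at Weeks 24 and 48. No reason is given. The 8-day allowance covers Visit 10/ET and OLE-6 (Table 1 note 5, 8.12, 7.20) but not Week 24.

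**What this does to the estimates.** Let r be the part of the follow-up value that is due to preceding probing.

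- Within an arm: observed change = true change + r.
- Between arms: observed difference = drug effect + (r_active − r_placebo).

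An r that is equal across arms cancels from a difference but remains in each arm's change.

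**Ratio scale, with assumed values.** Take a placebo load of 100 and an active load of 50, so the true ratio is 0.50.

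- Equal amount added to both arms, 50: (50 + 50)/(100 + 50) = 0.67.
- Equal amount added, 100: (50 + 100)/(100 + 100) = 0.75.
- Release proportional to load: the ratio stays at 0.50.

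An equal absolute addition therefore pulls a ratio towards no effect, while a proportional one leaves it alone.

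**Size, with assumed values.** The protocol gives no carry-over figure. If probing raised salivary DNA 2- to 10-fold, the within-arm shift would be log10(2) = 0.30 to log10(10) = 1.0. If the released material were also 20–30% lower on drug, with no other salivary effect:

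- 2-fold rise (load 1, release 1): log10(1.8/2) = −0.05 to log10(1.7/2) = −0.07.
- 10-fold rise (load 1, release 9): log10(8.2/10) = −0.09 to log10(7.3/10) = −0.14.

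The between-arm artefact would then be about 0.05–0.14 log10. Applying the 20–30% to the log shift itself would give 0.06–0.3 log10, but that treats release as scaling on the log scale. Released material adds on the natural scale, so the lower range is the better illustration.

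**The case against.** A reader might infer that the change in salivary *P. gingivalis* does mix drug effect with examination debris, and that the drug-placebo comparison is therefore confounded. The protocol does not support that reading, for these reasons.

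- **Randomisation.** The order is the same in all blinded arms. A common shift does not by itself create a difference between drug and placebo. Differential release is possible, because pocket depth and bleeding are sub-study outcomes that the drug might change, but nothing in the protocol shows it. If it occurred, it would partly reflect a real periodontal effect.
- **Week 48.** This is the endpoint time point, and the examination there may be days before the saliva sample, so same-day carry-over is not built in. Visit 2 saliva also follows the Screening examination by some days or weeks, so a Visit 2 to Week 48 comparison may be less asymmetric than the item numbers suggest.
- **Soft ordering.** The order applies only where feasible, and the lists are not strictly chronological. In 7.10 the 4-hour post-dose blood sample is item 2b, while the ECG at 1–1.5 hours is item 5.
- **Laboratory Manual.** It governs saliva collection, is not shown, and may already put saliva first.
- **Role of saliva.** It is not the only mechanism readout planned in all subjects. Blood and CSF biomarkers are listed too (4.1.2), and exploratory endpoints have no multiplicity control (11.3.2.4).

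All of this stands and limits the consequence. It does not remove the inconsistency. At Week 24 the two items are adjacent with the examination first, and a site that keeps to the list will sample saliva straight after probing. If the Laboratory Manual says otherwise, it conflicts with 7.7 and the protocol still needs correcting.

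**Conclusion.** The inconsistency in listed order is real, and its consequence is modest. Followed as written, the lists can contaminate the within-arm change in salivary *P. gingivalis* biomarkers at dental sites. The risk is clearest at Week 24 and uncertain at Week 48, where the interval since probing is left open. They can also add noise and make saliva data differ by site type.

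Bias in the drug-placebo comparison needs a further condition: release that differs by arm, or a ratio analysis with a roughly equal absolute addition in each arm. No size can be taken from the protocol. The figures above rest on an assumed 2- to 10-fold rise and an assumed 20–30% reduction in release, and they only show what would follow. That probing releases measurable material into saliva is itself an assumption, though a plausible one given the procedures described.

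The affected endpoint is exploratory, only selected sites are involved, and the co-primary endpoints are untouched. This is a low-priority improvement that is worth making because it is almost free.

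**What to change.** In 7.7 and 7.10, list saliva collection before the oral examination and oral sampling, as 7.1 already does. Add one sentence to 8.11: saliva is collected before any same-day periodontal probing or plaque sampling. Check that the Laboratory Manual says the same.

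The cost is the reordering of one item in each of two lists and one added sentence, with no extra visit, sample or staff time. Two limits remain. The change does not standardise the interval at Week 48 when the examination is done on an earlier day, and it cannot help samples already taken under the printed order.

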### **7.8 Study Treatment: Visit 8 (Day 224 $\pm$ 3)**

The following evaluations will be performed at this visit in the following order or as close as possible when feasible:

1. Concomitant medications;
2. Symptom-based physical examination;
3. Vital signs;
4. C-SSRS;
5. Blood/urine sample collection:
  - a. Safety laboratory tests; and
6. Adverse events.

### **7.9 Study Treatment: Visit 9 (Day 280 $\pm$ 8)**

Note: Please make every effort possible to have the visit scheduled in the morning so the AM dose can be taken in the morning. Ideally, daily doses should be taken 12 hours apart and no less than 6 hours apart.

The following evaluations will be performed at this visit in the following order as close as possible when feasible:

1. Administer study drug at the site
2. Blood/urine sample collection
  - a. Safety laboratory tests;
  - b. PK – A single post-dose sample will be drawn from each subject while on-site at the clinic at 3 hours  $\pm$  30 minutes post-dose. The exact times of AM dosing and PK sample collection at the site will be documented.
3. Adverse events;
4. 12-lead ECG 1-1.5 hours post-dose;
5. ADAS-Cog 11;
6. MMSE;

7. ADCS-ADL;
8. CDR-SB;
9. Concomitant medications;
10. Symptom-based physical examination;
11. Vital signs;
12. C-SSRS; and
13. Dispense study drug.

### **7.10 Study Treatment: Visit 10/Early Termination (Day 336 ± 8)**

Note: To accommodate the logistics of performing the LP procedure, it may be done up to 7 days prior to V10/Day 336. Please make every effort possible to have the visit scheduled in the morning so the AM dose can be taken in the morning. Ideally, daily doses should be taken 12 hours apart and no less than 6 hours apart.

The following evaluations will be performed at this visit or at Early Termination in the following order as close as possible when feasible:

1. Administer last dose of double-blind study drug at the site;
2. Blood/urine sample collection:
  - a. Safety laboratory tests;
  - b. PK - A single post-dose sample will be drawn from each subject while on-site at the clinic at 4 hours ± 30 minutes post-dose. The exact times of AM dosing and PK sample collections at the site will be documented.
  - c. Serum and whole blood (PBMCs) for biomarkers;
  - d. Pregnancy test (only if urine pregnancy test is positive);
3. Adverse events;
4. Oral examination and collection of oral biomarker samples (SGP and buccal cell swabs) at selected sites (will be completed within 8 days before Visit 10 [or Early Termination] when applicable).
5. 12-lead ECG 1-1.5 hours post-dose
6. MRI of the brain, only in subjects who had a screening MRI performed, and has to be done within 8 days prior to Visit 10. CT scans of the brain can be used instead of MRIs, only in subjects who have an absolute contraindication for MRI;
7. ADAS-Cog 11;
8. MMSE;
9. ADCS-ADL;
10. CDR-SB;
11. NPI;
12. Winterlight Speech Assessment (only in English speaking (primary language subjects and only in the US and UK);
13. Concomitant medications;
14. Symptom-based physical examination;
15. Saliva collection;

16. Weight;
  17. Vital signs;
  18. Lumbar puncture to collect CSF;
  19. Urine pregnancy test (women of child bearing potential only);
  20. C-SSRS;
  21. Informed consent will be obtained for subjects who agree to participate in the open label extension portion of the study; and
  22. Inclusion/exclusion will be evaluated to determine eligibility for subjects who want to participate in the open label extension portion of the study.  
Dispense OLE study drug – subjects who participate in OLE only. The subject should be instructed to take the first dose of COR388 in the morning of the next day.
- NOTE:** Effective 16 February 2021, the OLE portion of the study was terminated by the Sponsor.

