
 
1. Visit 10/ET MRI will be done only in subjects who had a screening MRI performed and may be done up to 8 days prior to Visit 10/ET. CT scans of the brain can be used instead of MRIs, only in subjects who have an absolute contraindication for MRI.
 
2. Administer the first MMSE as early in the screening period as possible. MMSE score should be <math>\geq 12</math> and <math>\leq 24</math> at both screening and Visit 2, and a <math>\leq 3</math>-point difference between visits, for inclusion in the study.
 
3. Oral biomarker samples include subgingival plaque and buccal cell swabs (only at selected sites).
 
4. Subjects will have follow-up oral examinations at 24 and 48 weeks.
 
5. Visit 10/ET oral examinations may be completed up to 8 days prior to Visit 10 (or ET) when applicable.
 
6. Baseline (V2) LP must be done after the baseline MMSE score has been verified and subject's eligibility has been confirmed, and prior to the first dose of study drug. To allow flexibility of scheduling the LP procedure, the MMSE and then the LP may be performed up to 7 days prior to baseline V2. Likewise, the LP at Visit10/ET may be performed up to 7 days prior to the other visit procedures, even if the LP is outside the visit window. The LP procedures must be
 
																				

- performed as per SOC and site specific SOPs, if applicable (including imaging before and/or during the LP, if required).
7. A pre-dose trough sample will be drawn at all visits 2, 3, and 7 immediately prior to the AM dose, and the subject will then take their dose of study drug on-site. The exact times of AM dosing and PK sample collections at the site will be documented. A single post-dose sample will be drawn from each subject while on-site at the clinic per the following schedule: V2 30 minutes - 4 hours; V3 60 minutes ± 30 minutes; V7 2 hours ± 30 minutes; V9 3 hours ± 30 minutes; and V10/ET 4 hours ± 30 minutes.
  8. At visits when the subject takes their dose of study drug on-site, ECGs should be measured approximately 1-1.5 hours after dosing.
  9. At Visit 3 and Visit 7, ECGs will also be performed at trough (prior to dosing).

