### **8.21 Blood Pharmacokinetic (PK) Evaluations**

At Visit 2 a pre-dose trough sample will be drawn immediately prior to the AM dose. The subject will take their first dose at the site with the dose time and date recorded in the eCRF. A PK blood draw will be collected within the first 4 hours after the dose (at any time between 30 minutes to 4 hours post-dose).

At Visit 3, Visit 7, Visit 9, and Visit 10 (or Early Termination), subjects will return to the clinic prior to taking their AM dose. A pre-dose trough sample will be drawn at Visit 3 and Visit 7 immediately prior to the AM dose. The subjects will then take their dose of study drug on-site and the exact time of the dose ingestion will be recorded. A single post-dose sample will be drawn from each subject while on-site at the clinic at 60 minutes  $\pm$  30 minutes, and at 2 hours  $\pm$  30 minutes, respectively.

At Visit 9 and Visit 10 single post dose sample will be drawn from each subject while on-site at the clinic at 3 hours  $\pm$  30 min and at 4 hours  $\pm$  30 min, respectively. The exact time of the last dose of study drug will be recorded.

In all cases, the exact clock time of each PK sample will be recorded.

Plasma samples will be quantified for COR388 (and potential metabolites of interest). Data will be analyzed by a population pharmacokinetic approach to derive COR388 (and potential metabolites of interest) systemic exposure metrics. A

detailed population PK analysis plan will be generated and finalized prior to the PK analysis being initiated.

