## 8.23 Electrocardiograms (ECGs)

Standard 12-lead electrocardiograms (ECGs) will be performed at Screening (Visit 1), Visit 2, Visit 3, Visit 4, Visit 5, Visit 7, Visit 9, Visit 10 (or Early Termination), and Visit 11 (Safety Follow-up Visit). The Investigator will review ECGs for any changes from baseline. At Visit 2, Visit 3, Visit 7, Visit 9, and Visit 10 (or Early Termination), subjects will take their dose on-site and the exact time of the dose ingestion will be recorded. The time to maximum plasma concentration of COR388 ( $T_{max}$ ) is approximately 1-1.5 hours. At visits when the subject takes their dose of study drug on-site, ECGs should be measured approximately 1-1.5 hours after dosing. At Visit 3 and Visit 7, ECGs will also be performed at trough (prior to dosing). ECGs will be reviewed by a cardiologist at the central ECG laboratory to identify any abnormalities and verify automatically calculated values of RR, PR, QRS, and QTc intervals. Clinically significant ECG events and abnormalities will be recorded as adverse events.

Open Label Extension: Standard 12-lead ECGs will be performed at Visits OLE-1, OLE-2, OLE-4, OLE-6 (or Early Termination) and OLE-9 (OLE Safety Follow-Up Visit). **NOTE:** Effective 16 February 2021, the OLE portion of the study was terminated by the Sponsor.

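### The shared Visit 10/Early Termination list opens with an on-site dose, but subjects stopped for a drug-related safety reason are sent to that list and barred from further drug

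*Protocol*

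**What the plan says.** Protocol section 7.10 covers both visits with a single lead-in: "The following evaluations will be performed at this visit or at Early Termination in the following order". Item 1 is "1. Administer last dose of double-blind study drug at the site". Item 2b is a PK sample to be taken "on-site at the clinic at 4 hours ± 30 minutes post-dose", and item 5 is an ECG 1 to 1.5 hours after the dose.

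Three other places carry the dose or its timing to Early Termination:

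- Section 8.23: "Visit 10 (or Early Termination), subjects will take their dose on-site and the exact time of the dose ingestion will be recorded".
- Section 8.21: "Visit 10 (or Early Termination), subjects will return to the clinic prior to taking their AM dose".
- Table 1, footnote 7, PK time: "V10/ET 4 hours ± 30 minutes".

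Section 12.13 deals with subjects who stop the investigational product for safety reasons related to it. They may not resume it. They are followed until the safety concern or adverse event has stabilized or resolved. Their participation is then ended early, and the Visit 10/Early Termination procedures are mandatory. Section 9.1.5 states separately that re-challenge is not allowed after such a stop.

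The synopsis (Safety Follow-up Period) and section 7.12 also send every early-termination subject to the Week 48 procedures, without separating those still on drug from those already off it.

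**The concern.** Section 12.13 fixes a sequence: drug stopped, no resumption, follow-up until stable or resolved, then the Visit 10/Early Termination procedures. A subject on that path is off drug on reaching the list, and the first item on the list is a dose of the drug that 12.13 withholds. The two instructions cannot both be carried out as written for that subject.

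The group is one that the protocol foresees. Section 12.13 gives transaminase elevations as its example, and section 8.24 lists liver criteria for stopping treatment. A visit list that calls for a dose which another section forbids to these subjects is a safety-relevant inconsistency, even if sites are likely to resolve it sensibly. Sites also have no instruction on what becomes of a PK sample and an ECG that are timed from a dose that is not given, so practice may differ between sites.

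**Working it through.** No arithmetic on power, alpha or sample size applies. The check sets the passages side by side.

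**Step 1: whom the list covers.** The lead-in of 7.10 names Visit 10 and Early Termination together. It goes on to say that the order should be kept as closely as feasible. That qualifier governs the order of the items; it exempts nobody from an item.

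**Step 2: whether the dose-linked items carry a condition.** Section 7.10 has 22 numbered items. Counting 2a to 2d separately gives 22 − 1 + 4 = 25 entries.

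| Type of entry | Entries | Count |
|---|---|---|
| With a subject or site condition | 2d, 4, 6, 12, 19, 21, 22 | 7 |
| Dose-linked | 1, 2b, 5 | 3 |
| Dose-linked with a condition on treatment status | none | 0 |

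Item 6 shows the form such a condition takes: "only in subjects who had a screening MRI performed".

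**Step 3: the state of the subject at the visit.** Under 12.13 the procedures come after the follow-up, which comes after the stop. With resumption barred, the subject is off drug at the visit.

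**Step 4: each dose-linked item for that subject.**

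| Entry in 7.10 | Without a dose | Relation to 12.13 and 9.1.5 |
|---|---|---|
| 1, on-site dose | cannot be done | direct conflict |
| 2b, PK sample 4 hours after the dose | blood can be drawn, but not at the stated time | timing undefined; no breach |
| 5, ECG 1 to 1.5 hours after the dose | can be recorded, but not at the stated time | timing undefined; no breach |

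Only item 1 meets the bar. For item 5, Table 1 footnote 8 ties the ECG timing to visits where a dose is taken on-site, so an ECG without a dose remains possible. For item 2b, section 8.21 has the clock time of every PK sample recorded and uses a population PK approach, so an omitted or differently timed sample is a matter of data collection.

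**Step 5: how far the other sections reach.** Section 8.23 states the on-site dose at Early Termination outright. Section 8.21 has subjects arrive before their morning dose at Early Termination. Its later sentence, "The subjects will then take their dose of study drug on-site and the exact time of the dose ingestion will be recorded", follows the trough samples of Visits 3 and 7 and precedes the post-dose times for those two visits, so it does not clearly reach Early Termination and is not relied on here. Footnote 7 sets a post-dose PK time for the combined visit.

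**The case against.** The best case on the other side is that the protocol already settles whether to dose. Sections 12.13 and 9.1.5 are explicit and specific to this group, while item 1 is a general visit-list line. Four further points support that view:

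- Item 1 speaks of the last dose, and a barred subject has already taken it.
- Section 8.5 dispenses no blinded drug after Visit 9.
- Section 12.13 itself later refers to the Visit 10/Early Termination assessments, and giving a dose is not an assessment.
- Treatment status is governed centrally elsewhere: section 7.9 also lists an on-site dose without a condition, although dosing must be halted when liver tests are missed.

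Much of this stands. It makes an actual re-dose unlikely, and it is why the point stays small. It does not remove the conflict:

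- No passage says that the bar overrides the list, or that the reference to a last dose releases subjects already off drug.
- Section 8.23 names Early Termination as a dosing visit without that phrase.
- The end of dispensing at Visit 9 does not cover a subject who stops earlier and still holds capsules; section 5.6 has containers brought back at each visit.
- The comparison with section 7.9 is incomplete, because 12.13 sends barred subjects to Visit 10/Early Termination by name.
- The word assessments stands beside a requirement, in the same section, for procedures.

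A reader might infer that the protocol intends to re-dose subjects stopped for a safety reason, or that this is likely to happen. The documents do not support that: the bar is stated twice and is more specific than the list. A reader might also infer that the PK sample and the ECG breach the bar. They do not; they only lose their timing.

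**Conclusion.** The inconsistency is real and lies in the text. For subjects already off drug for a safety reason related to the investigational product, item 1 of section 7.10 and the on-site dose in section 8.23 conflict with sections 12.13 and 9.1.5. Items 2b and 5, with Table 1 footnote 7, have no defined timing for them.

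Its size is one entry in direct conflict and two that cannot be timed as worded, out of 25 entries. Subjects who complete treatment, and early terminators still taking drug, are not affected. The number of subjects concerned cannot be derived, because the protocol gives no rate of such stops. The probability of an actual re-dose is judged low, on the assumption that investigators follow the specific bar. Nothing here bears on the endpoints, alpha or power.

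**What to change.** Reconcile sections 7.10, 8.21 and 8.23 and Table 1 footnote 7 with sections 12.13 and 9.1.5. State which dose-linked Visit 10/Early Termination items (on-site dose, post-dose PK sample, ECG timing) apply to subjects still on drug and which to subjects already off drug. The same statement should govern the references to Week 48 procedures in the synopsis and section 7.12. The clinical rule itself is for the sponsor to set. The cost is a wording change in a protocol amendment, with no cost to the analysis.
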